16. INTERIM AND FINAL ANALYSIS

16.1 Interim Analysis (DSMC Review meeting)

An unscheduled DSMC review meeting of all available unblinded preliminary safety study data will be conducted when any stopping rules (Protocol Section 4.6) are met in two or more patients. All stopping rules will be listed by treatment group.

Two DSMC Review meeting are scheduled:

1. DSMC Safety Review Meeting on all available unblinded preliminary safety study data:
Safety assessment when 40.8% (n=20 out of 49) patients reach week 8 resulting in a decision on continuation of the study based on safety (Go/No go decision); enrolment would remain ongoing during this review.
2. DSMC Safety Review and Futility Analysis Meeting on all available unblinded preliminary virology, safety, PK and PD study data:
Safety and futility when 50% patients (n=25) reached week 12, resulting in a decision on continuation of the study (Go/No go decision) based on safety and evidence of a benefit of EYP001 (HBsAg, other secondary viral markers); enrolment is ongoing during this review.

The DSMC review meeting will be performed on all available primary and secondary endpoints according to the DSMC charter, which describes the overall guidelines, composition, roles, and responsibilities of the independent DSMC for the EYP001-201 study, including the selection of DSMC members, timing of meetings, methods of providing information to and from the DSMC, frequency and format of meetings, data analysis recommendations, and DSMC relationships with other parties participating in the conduct of this study.

The futility assessment will be performed to determine if EYP001 has no benefit at a point when 50% of patients have reached 12 weeks of dosing. The futility assessment will be performed by the DSMC according to the following rules:

- A treatment effect of -1.0 on a log₁₀ scale of HBsAg for the primary endpoint at 16 weeks, and a common standard deviation of 1.08 was assumed and the treatment effect would be -0.5 after 12 weeks of treatment, with common standard deviation of 0.7 Using a one-sided alpha of 0.05 and 80% power (beta = 0.20), a group sequential design, incorporating a futility and efficacy O'Brien-Fleming analysis when 50% of patients have reached 12 weeks of treatment, needs inclusion of 49 patients.
- Table 2 gives the probability of stopping early under the null and alternative hypothesis, at the time of the interim analysis.

The probability of stopping correctly for futility is 40%. The probability of stopping wrongly for futility is only 3.5%.

Under H ₀		Under H _a	
Efficacy	Futility	Efficacy	Futility
0.001	0.4	0.073	0.035

H₀: Null Hypothesis; H_a: Alternative Hypothesis

- The efficacy boundary is crossed when the 12-week p-value is less than 0.001, or the difference is less than -0.971 on a log scale. The futility boundary is crossed when the 12-week p-value is higher than 0.603, or the difference is more than 0.085 on a log scale.

The stopping of the study for futility will be considered by the DSMC by applying these rules. The study will not stop for efficacy at Week 12 DSMC Safety Review and Futility Analysis Meeting even if

efficacy boundary is crossed. The criteria are not binding and DSMC can overrule after overall consideration.

Data will be summarized and presented by treatment group and time point in summary tables. Descriptive statistics including number of patients (N), means, standard deviations, medians, and minimum and maximum values will be presented for continuous variables. Counts and percentages will be presented for categorical variables. In addition, by- patient listing for all safety and efficacy data will be presented.

Note that all DMSC review meeting will be descriptive, except 2nd scheduled DSMC safety and futility review meeting containing mentioned futility testing.

Based on the protocol clarification letter #13, the first interim analysis as described in the current EYP001-201 Study Protocol v3.0 dated 29th January 2020 corresponds to the first planned DSMC meeting and is performed on all available preliminary safety study data at the time of database snapshot (20 patients reach week 8, expected by 1st March 2021 with data cut-off point defined to be 5th March 2021.). Safety data only will be evaluated, based upon the review of the individual values (clinical significant abnormalities), descriptive statistics (summary tables, graphics) and if needed.). The term “first interim analysis” should be replaced by “DSMC Safety Review Meeting”. The “second interim analysis” corresponds to the second planned DSMC meeting covering safety review and futility analysis and is performed on all available virology, safety, PK and PD study data at the time of database snapshot when 25 patients have reached w12 (expected by 16th March 2021 with data cut-off point defined to be 15th May 2020). Safety and futility will be evaluated, based upon the review of the individual values (clinical significant abnormalities), descriptive statistics (summary tables, graphics) and on statistical analysis (futility analysis as described in section 11.5 of the study protocol). The term “second interim analysis” should be replaced by an interim analysis corresponding to “DSMC Safety and Futility Review Meeting”

There will be an additional database lock performed on all patient visits to Week 16 / Visit 9 for all randomised patients. All patients will be unblinded following database lock. Novotech Biostatistician will convert the datasets to CDISC format. Novotech data management will provide ENYO with raw data and Biostatistician will provide ENYO with CDISC converted datasets.

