2.5 Randomization

Sequential screening numbers will be assigned to patients at the time of informed consent signing. As they are enrolled into the study and after eligibility on Day -3 at the earliest and prior to dosing on Day 1 at the latest, patients will be assigned to a unique randomization number which are randomly assigned to treatment according to the specified randomization scheme.

The randomization schedule will be computer-generated before the start of the study.

An Interactive Web Response System (IWRS) will be employed to manage patient and treatment assignments.

Patients will be randomized prior to study drug (EYP001a or placebo and NA) administration on Day 1 in the ratio of approximately 3:1 (37:12) into 2 arms:

- Experimental Arm: EYP001a 200 mg QD + NA daily (37 patients)
- Control Arm: Placebo + NA daily (12 patients)

The ratio will be controlled through block randomization.

Patients will also be stratified per HBeAg status, based on medical history HBeAg value or established during screening, to obtain a balanced randomization to both study arms.

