18. TABLES

Table Number	Table Title	Population	DSMC Safety	DSMC Safety and Futility
14.1	Demographics and Other Baseline Characteristics			
14.1.1	Summary of Participant Enrolment and Disposition	ITT	X	X
14.1.2.1	Summary of Demographics and Baseline Characteristics	ITT		
14.1.2.2	Summary of Demographics and Baseline Characteristics	mITT		
14.1.2.3	Summary of Demographics and Baseline Characteristics	Safety	X	X
14.1.2.4	Summary of Demographics and Baseline Characteristics	PP		
14.1.3.1	Summary of Viral Serology at Screening	ITT		
14.1.3.2	Summary of Viral Serology at Screening	mITT		
14.1.3.3	Summary of Viral Serology at Screening	Safety		
14.1.3.4	Summary of Viral Serology at Screening	PP		
14.1.4	Summary of Treatment Compliance	Safety	X	X
14.2	Efficacy			
14.2.1.1.1	Summary of HBsAg by A Genotype – Imputation	ITT		X
14.2.1.1.2	Summary of HBsAg by A Genotype – No imputation	ITT		X
14.2.1.2.1	Summary of HBsAg by A Genotype – Imputation	mITT		
14.2.1.2.2	Summary of HBsAg by A Genotype – No Imputation	mITT		

14.2.1.3.1	Summary of HBsAg by A Genotype - Imputation	PP		
14.2.1.3.2	Summary of HBsAg by A Genotype – No Imputation	PP		
14.2.2.1.1	Analysis of HBsAg: Baseline to Week 16 – Imputation	ITT		X
14.2.2.1.2	Analysis of HBsAg: Baseline to Week 16 – No Imputation	ITT		X
14.2.2.2.1	Analysis of HBsAg: Baseline to Week 16 - Imputation	mITT		
14.2.2.2.2	Analysis of HBsAg: Baseline to Week 16 – No Imputation	mITT		
14.2.2.3.1	Analysis of HBsAg: Baseline to Week 16 – Imputation	PP		
14.2.2.3.2	Analysis of HBsAg: Baseline to Week 16 – No Imputation	PP		
14.2.3.1	Summary and Analysis of HBsAg Loss Rate A	ITT		X
14.2.3.2	Summary and Analysis of HBsAg Loss Rate B	ITT		X
14.2.4.1	Summary and Analysis of HBsAg Responder Rate A	ITT		X
14.2.4.2	Summary and Analysis of HBsAg Responder Rate B	ITT		X
14.2.5	Summary of HBsAg Relapse Rate	ITT		
14.2.6	Summary of Virologic Failure Rate of HBV DNA	ITT		X
14.2.7	Summary of HBV-pgRNA	ITT		X
14.2.8	Summary of HBcrAg	ITT		X
14.2.9	Summary of HBeAg	ITT (HBeAg+ patients)		X
14.2.10	Summary of Fibroscan VCTE	ITT		X
14.2.11	Summary of HBsAg Loss Rate (Target not detected vs. Target detected)	ITT		

14.2.12	Summary of Anti-HBs	ITT		
14.2.13	Summary of Anti-HBe	ITT		
14.2.14	Summary of PD Markers	PD		
14.3	Safety			
14.3.1	Summary of Concomitant Medication	Safety	X	X
14.3.3	Adverse Events			
14.3.3.1	Summary of Overall Treatment Emergent Adverse Events	Safety	X	X

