LS mean is derived from a general linear model for repeated measures. The covariates are treatment groups, visit, baseline HBsAg, A Genotype, HBeAg positive and the interaction term of treatment group*visit.

Covariance structure is XXX.

CI = Confidence Interval. SE = Standard Error.

Programming Note:

- Repeat for table 14.2.2.1.2 (ITT set with no imputation), 14.2.2.2.1 (mITT with imputation), 14.2.2.2.2 (mITT with no imputation), 14.2.2.3.1 (PP set with imputation) and 14.2.2.3.2 (PP set with no imputation) .

-The SAS code used to implement this analysis is given below:

```
PROC MIXED DATA=dataset;
  CLASS ID TRT VISIT HBeAg;
  MODEL CHG = Baseline HBeAg TRT VISIT TRT*VISIT / SOLUTION CL;
  DDFM=KenwardRoger;
  REPEATED VISIT /SUBJECT = ID TYPE = UN ;
  LSMEANS TRT*VISIT / DIFF CL;
  RUN;
```

Table 14.2.3.1 Summary and Analysis of HBsAg Loss Rate A (ITT Set)

Visit	Category	Statistics	EYP001a 200 mg QD + NA daily (N=XXX)	Placebo + NA daily (N=XXX)
Week 16		n	xx	xx
	HBsAg Loss	n (%) [1]	xx (xx.x %)	xx (xx.x %)
		p-value	0.XXX	

<Repeat for Week 40>

Source Listing: 16.2.6.1

p-value is based on the Person Chi-squared Test.

HBsAg Loss is defined as HBsAg value < LLOQ/TND.

[1] Number of subjects at each visit (Visit n) will be used as the denominator for the calculation of all percentages.

Programming Note:

- Only present Week 16 and Week 40 will consider multiplicity by a combination of a hierarchical fixed test procedure and a Hochberg procedure to adjust p-value.

Table 14.2.3.2 Summary and Analysis of HBsAg Loss Rate B (ITT Set)

Visit	Category	Statistics	EYP001a 200 mg QD + NA daily (N=XXX)	Placebo + NA daily (N=XXX)
Week 16		n	xx	xx
	HBsAg Loss	n (%) [1]	xx (xx.x %)	xx (xx.x %)
		p-value	0.XXX	

<Repeat for Week 40>

Source Listing: 16.2.6.1

p-value is based on the Person Chi-squared Test.

HBsAg Loss is defined as HBsAg value < LLOQ/TD.

[1] Number of subjects at each visit (Visit n) will be used as the denominator for the calculation of all percentages.

Programming Note:

- Only present Week 16 and Week 40 will consider multiplicity by a combination of a hierarchical fixed test procedure and a Hochberg procedure to adjust p-value.

Table 14.2.4.1 Summary and Analysis of HBsAg Responder Rate A (ITT Set)

Visit	Category	Statistics	Decrease from Baseline \geq 1.0 on the log10 Scale	
			EYP001a 200 mg QD + NA daily (N=XXX)	Placebo + NA daily (N=XXX)
Week 16	HBsAg Responder	n		
		n (%) [1]		
		p-value		
Week 40		n	xx	xx

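### The futility cut-off p > 0.603 is a one-sided, lower-tail value, but the rule names no tail and the SAS code for the futility-meeting tables gives a two-sided p by default

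*SAP*

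**What the plan says.** SAP 16.1 builds the futility rule on a one-sided design: "Using a one-sided alpha of 0.05 and 80% power (beta = 0.20), a group sequential design". Its Week 12 assumption is that "the treatment effect would be -0.5 after 12 weeks of treatment, with common standard deviation of 0.7". The look takes place as follows: "Safety and futility when 50% patients (n=25) reached week 12". Allocation is "in the ratio of approximately 3:1 (37:12) into 2 arms" (SAP 2.5).

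The rule itself reads "The futility boundary is crossed when the 12-week p-value is higher than 0.603, or the difference is more than 0.085 on a log scale", and protocol 11.5 carries the same sentence. The printed probability of crossing for futility is 0.4 under H0 and 0.035 under Ha. The second figure is put into words as "The probability of stopping wrongly for futility is only 3.5" per cent. The efficacy limits are p below 0.001 or a difference below -0.971, with crossing probabilities of 0.001 and 0.073. The DSMC may overrule the criteria.

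On sidedness, protocol 11.1 makes one-sided testing the default. SAP 3.3 applies a one-sided 5% test to the HBsAg model and asks for the treatment comparison at that level at every visit, Week 12 included.

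On output, SAP 18 marks Tables 14.2.2.1.1 and 14.2.2.1.2, "Analysis of HBsAg: Baseline to Week 16" (with and without imputation), for the futility meeting. Their shell has a row labelled only p-value, next to a 95% confidence interval. The programming note obtains the comparison with "LSMEANS TRT*VISIT / DIFF CL". SAP 3.5 combines the imputed results with PROC MIANALYZE.

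**The concern.** A futility cut-off near 0.6 means very different things on the two scales. A lower-tail one-sided p above 0.5 says that the estimate favours placebo. A two-sided p above 0.6 says only that the estimate is close to zero, on either side. Going from one to the other is not simple halving, because the conversion depends on the sign of the estimate.

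The rule leaves the tail to be inferred, and the code written for the relevant tables has no step that produces a one-sided p. A programmer who follows the code, or a DSMC member who compares the printed p with 0.603, could flag a result that favours EYP001a. The error rates quoted beside the rule would not describe that decision. This is the plan's only statistical go/no-go boundary that can recommend stopping, so its cut-off should match the number put in front of the committee.

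**Working it through.** **Inputs.** Week 12 effect -0.5, SD 0.7 and n = 25 (SAP 16.1); allocation 3:1 (SAP 2.5), so 18.75 and 6.25 per arm, or 19 and 6 in whole patients. The method is a two-sample normal approximation.

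**Standard error.** SE = 0.7 × √(1/18.75 + 1/6.25) = 0.7 × √0.2133 = 0.323.

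**Reproducing the printed figures, one-sided lower tail** (p = Φ(difference/SE)):
- Futility limit: 0.085/0.323 = 0.263, and Φ(0.263) = 0.604 (printed 0.603).
- Futility under H0: 1 − 0.604 = 39.6% (printed 40%).
- Futility under Ha: P(Z > (0.085 + 0.5)/0.323) = P(Z > 1.81) = 3.5% (printed 3.5%).
- Efficacy limit: −0.971/0.323 = −3.00, one-sided p = 0.0013 (printed 0.001).
- Efficacy under Ha: P(Z < (−0.971 + 0.5)/0.323) = P(Z < −1.46) = 7.3% (printed 0.073).

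All the printed values are recovered. The two-sided p at +0.085 would be 2 × (1 − 0.604) = 0.79, so 0.603 cannot be a two-sided cut-off. Using the Week 16 SD of 1.08 instead gives 12.0% for futility under Ha, which does not match, so the rule was built on SD 0.7.

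**If 0.603 is compared with a two-sided p.** Two-sided p > 0.603 means |z| < 0.520, so |difference| < 0.520 × 0.323 = 0.168.

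| Reading | H0 | Ha (−0.5) |
|---|---|---|
| One-sided p (as designed) | 39.6% | 3.5% |
| Two-sided p alone | 39.7% | 13.3% |
| Two-sided p, or difference > 0.085, read literally | 69.9% | 15.2% |

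- Two-sided p alone, Ha: the limits ±0.168 become (−0.168 + 0.5)/0.323 = 1.03 and (0.168 + 0.5)/0.323 = 2.07. P(1.03 < Z < 2.07) = 13.3%.
- Literal 'or': the two conditions together cover every difference above −0.168. Under Ha this is P(Z > 1.03) = 15.2%; under H0 it is P(Z > −0.520) = 69.9%.
- With 19:6 the Ha figures are 3.7%, 13.7% and 15.7%. A t-based calculation changes the p-alone figure only slightly (13.4% to 13.8%).

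The H0 rate on two-sided p alone looks unchanged because a null p-value is uniform (1 − 0.603 = 0.397). The trials flagged are different ones, however: a band around zero instead of the side that favours placebo.

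**Example.** A favourable difference of −0.15 gives z = −0.15/0.323 = −0.464. Its one-sided p is 0.32, well short of 0.603. Its two-sided p is 2 × 0.32 = 0.64, which crosses.

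**The case against.** The strongest reply is that the text already settles the tail. The design in SAP 16.1 is one-sided, SAP 3.3 requires a one-sided comparison for this model at Week 12, and protocol 11.1 makes one-sided testing the default. The SAP appears to set sidedness in words and not in code: the same PROC MIXED template serves the liver fibrosis analysis, which SAP 3.3 specifies as two-sided. The template is not production code either, since a semicolon closes the MODEL statement before the degrees-of-freedom option. The limit of +0.085 has no tail, and 'or' can be read as restating one limit on a second scale. A two-sided p would then visibly disagree with it. The rule is also non-binding, and neither SAP 16.1 nor protocol 11.5 names Table 14.2.2.x as the source of the p-value. The DSMC charter, which is not among these documents, may do so.

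Much of this stands. A reader might infer that the DSMC table prints a two-sided p, but the documents do not say so. The shell says only p-value, and the two-sided result rests on how the SAS procedures behave by default. A reader might also infer that the printed 40% and 3.5% are wrong. They are correct for the one-sided design.

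What the reply does not do is join the text to the output. A one-sided significance level does not tell a programmer to print a signed lower-tail p. If the two limits disagree, the rule does not say which governs. The limits are joined by 'or', so a literal reading lets the p-value alone trigger the flag.

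**Conclusion.** The point holds as a mismatch between the decision threshold and the code specified for the tables that go to the futility meeting. The threshold is one-sided and does not say so; the code returns a two-sided p unless someone adds a conversion.

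If the unconverted p were used, the flag rate at the planned Week 12 effect would be about 13% on p alone, or about 15% under the literal 'or', against the printed 3.5%: roughly four times as high (13.3/3.5 = 3.8; 15.2/3.5 = 4.3). The rise under H0 from 40% to about 70% needs the literal 'or'. These figures assume the SAS default p is carried over unchanged, that Tables 14.2.2.1.1 and 14.2.2.1.2 supply the p-value, and the planned SD 0.7 with 25 patients at 3:1.

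Two further inferences should not be drawn. This is not the trial's only formal stopping rule: protocol 4.6 has safety stopping and pausing rules. Nor should a loss of overall power at 37:12 be quoted. The rule is non-binding, and SAP 15 records that enrolment was suspended after about 25 randomizations, so power at 49 patients no longer describes this trial.

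**What to change.** 1. In SAP 16.1 and protocol 11.5, state that the futility limit is crossed when the one-sided lower-tail p-value for EYP001a minus placebo at Week 12 exceeds 0.603, equivalently when the difference exceeds +0.085. The equivalence holds at the planned SE of 0.323, so also say which scale governs if the observed SE differs.
2. In the DSMC versions of Tables 14.2.2.1.1 and 14.2.2.1.2, add to the Week 12 row a p-value labelled as one-sided. Compute it as the t (or normal) cumulative distribution function of estimate/SE, and keep the sign as EYP001a minus placebo.
3. Add a note that the boundary is not to be applied to the default p-value from LSMEANS or MIANALYZE.

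The cost is one sentence in each document, one line of code and a label. The design, the data collected and patient procedures do not change.

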16.2 Final Analysis (End of Study)

The final analysis will be conducted after all participants have completed the study (at the end of the study), the clinical database has been hard locked, the analysis populations have been approved and the study has been unblinded.

The final analysis will be based on the final version of the SAP. Any deviations from the planned analysis will be documented in the CSR.

17. SOFTWARE

- SAS[®] Version 9.2 or higher (SAS Institute, Cary, North Carolina, USA).

18. TABLES

Table Number	Table Title	Population	DSMC Safety	DSMC Safety and Futility
14.1	Demographics and Other Baseline Characteristics			
14.1.1	Summary of Participant Enrolment and Disposition	ITT	X	X
14.1.2.1	Summary of Demographics and Baseline Characteristics	ITT		
14.1.2.2	Summary of Demographics and Baseline Characteristics	mITT		
14.1.2.3	Summary of Demographics and Baseline Characteristics	Safety	X	X
14.1.2.4	Summary of Demographics and Baseline Characteristics	PP		
14.1.3.1	Summary of Viral Serology at Screening	ITT		
14.1.3.2	Summary of Viral Serology at Screening	mITT		
14.1.3.3	Summary of Viral Serology at Screening	Safety		
14.1.3.4	Summary of Viral Serology at Screening	PP		
14.1.4	Summary of Treatment Compliance	Safety	X	X
14.2	Efficacy			
14.2.1.1.1	Summary of HBsAg by A Genotype – Imputation	ITT		X
14.2.1.1.2	Summary of HBsAg by A Genotype – No imputation	ITT		X
14.2.1.2.1	Summary of HBsAg by A Genotype – Imputation	mITT		
14.2.1.2.2	Summary of HBsAg by A Genotype – No Imputation	mITT		

14.2.1.3.1	Summary of HBsAg by A Genotype - Imputation	PP		
14.2.1.3.2	Summary of HBsAg by A Genotype – No Imputation	PP		
14.2.2.1.1	Analysis of HBsAg: Baseline to Week 16 – Imputation	ITT		X
14.2.2.1.2	Analysis of HBsAg: Baseline to Week 16 – No Imputation	ITT		X
14.2.2.2.1	Analysis of HBsAg: Baseline to Week 16 - Imputation	mITT		
14.2.2.2.2	Analysis of HBsAg: Baseline to Week 16 – No Imputation	mITT		
14.2.2.3.1	Analysis of HBsAg: Baseline to Week 16 – Imputation	PP		
14.2.2.3.2	Analysis of HBsAg: Baseline to Week 16 – No Imputation	PP		
14.2.3.1	Summary and Analysis of HBsAg Loss Rate A	ITT		X
14.2.3.2	Summary and Analysis of HBsAg Loss Rate B	ITT		X
14.2.4.1	Summary and Analysis of HBsAg Responder Rate A	ITT		X
14.2.4.2	Summary and Analysis of HBsAg Responder Rate B	ITT		X
14.2.5	Summary of HBsAg Relapse Rate	ITT		
14.2.6	Summary of Virologic Failure Rate of HBV DNA	ITT		X
14.2.7	Summary of HBV-pgRNA	ITT		X
14.2.8	Summary of HBcrAg	ITT		X
14.2.9	Summary of HBeAg	ITT (HBeAg+ patients)		X
14.2.10	Summary of Fibroscan VCTE	ITT		X
14.2.11	Summary of HBsAg Loss Rate (Target not detected vs. Target detected)	ITT		

14.2.12	Summary of Anti-HBs	ITT		
14.2.13	Summary of Anti-HBe	ITT		
14.2.14	Summary of PD Markers	PD		
14.3	Safety			
14.3.1	Summary of Concomitant Medication	Safety	X	X
14.3.3	Adverse Events			
14.3.3.1	Summary of Overall Treatment Emergent Adverse Events	Safety	X	X
14.3.3.2	Summary of Treatment Emergent Adverse Events by SOC and PT	Safety	X	X
14.3.3.3	Summary of Serious Treatment-Emergent Adverse Events by SOC and PT	Safety	X	X
14.3.3.4.1	Summary of Treatment-Emergent Adverse Events by Relationship to Study Drug by SOC and PT	Safety	X	X
14.3.3.4.2	Summary of Treatment-Emergent Adverse Events by Relationship to ETV by SOC and PT	Safety		
14.3.3.4.3	Summary of Treatment-Emergent Adverse Events by Relationship to TD by SOC and PT	Safety		
14.3.3.5	Summary of Treatment-Emergent Adverse Events by SOC, PT and Severity	Safety	X	X
14.3.3.6	Summary of Treatment Emergent Adverse Events Leading to Study Drug Discontinuation by SOC and PT	Safety	X	X
14.3.4	Laboratory Parameters			
14.3.4.1.1	Summary of Hematology & Coagulation	Safety	X	X
14.3.4.1.2	Summary of Hematology & Coagulation Shifts from Baseline	Safety		
14.3.4.2.1	Summary of Serum Chemistry	Safety	X	X

14.3.4.2.2	Summary of Serum Chemistry Shifts from Baseline	Safety		
14.3.4.3.1	Summary of Lipid Metabolic Profile	Safety	X	X
14.3.4.3.2	Summary of Lipid Metabolic Profile Shifts from Baseline (Low, Normal, High)	Safety		
14.3.4.3	Summary of Urinalysis	Safety	X	X
14.3.4.4	Summary of Maximum CTCAE for ALT, AST, BILI and GGT for Post Treatment Assessments	Safety		X
14.3.5	Other Safety			
14.3.5.1	Summary of Vital Signs	Safety	X	X
14.3.5.2.1	Summary of 12-Lead ECG	Safety	X	X
14.3.5.2.2	Summary of 12-Lead ECG Interpretation	Safety	X	X
14.3.5.3	Summary of Pruritus Assessment - 5-D Pruritus Scale	Safety		
14.3.5.4	Summary of Pruritus Assessment - Visual Analogue Scale	Safety	X	X
14.3.5.5	Summary of Liver Fibrosis and Inflammation Assessment	Safety		
14.3.5.6	Analysis of Liver Fibrosis and Inflammation Assessment: Baseline to Week 16	Safety		X
14.3.5.7	Summary of Liver Imaging	Safety	X	X

